6.8 SAFETY ASSESSMENTS

Safety assessments for the trial drug will occur at 2-weekly intervals in the first month after randomisation and six-monthly intervals thereafter during the 18 months duration of the trial.

The local hospital sites will ask participants by phone about the presence of symptoms that might be related to taking the trial drugs (e.g., headache, bleeding) during the first month after randomisation
The central blinded trial co-ordinators will continue to ask participants about the IMP symptoms as a part of the postal questionnaire at 6, 12 and 18-months follow-up visits.

The local hospital sites will phone-visit participants at 2-weekly intervals in the first month, and at 6, 12, and 18-month follow-up visits to ask about adherence to trial medication.

Investigators from the local hospital sites and central trial co-ordinators will record and report the outcome and safety events including SAEs, SARs and SUSARs between randomisation and the last follow-up visit at 18 months based on the information from the follow-up questionnaires as well as alerts from the hospital records. The safety reporting will include two weeks after the last dose of IMP is administrated.

The IMP symptoms, drug adherence, outcome, and safety events will be recorded in the eCRF. The SAEs, SARs and SUSARs will be reported to the sponsor.

6.9 STUDY ASSESSMENTS

Study assessments (see Table 2) include the maximum of the six planned study visits.

The first study visit includes consent, baseline information collection and randomisation. After eligibility confirmation and obtaining the informed consent, investigators will collect the baseline medical history data required for randomisation. The randomisation visit can take place on the same day as the consent visit at the clinic, if all required tests for eligibility criteria and the baseline information are available.

Baseline information will include the confirmation of eligibility and informed consent details, demographic information such as date of birth, sex assigned at birth, ethnicity, years of full-time education ^{62, 63} and occupation.

The medical history will contain details of incident stroke, past medical history, vascular risk factors, concomitant medications and the characteristics of the lacunar stroke and SVD features (white matter hyperintensities/hypoattenuation, and/or lacunes) on brain imaging.

Baseline brain MR (preferred wherever possible) or CT: To identify the index stroke or exclude other causes of symptoms, and assess the burden of SVD – this is the clinical scan with MRI (T2, FLAIR, T1, T2* or SWI and diffusion imaging) or CT obtained soon after the presentation with stroke to diagnose the stroke. Brain imaging in eligible patients with lacunar ischaemic stroke may show either:

- a recent, relevant (in time and location) acute small subcortical (lacunar) infarct,

- or, if no visible acute lacunar infarct, there is no other competing pathology as a cause for stroke (e.g. no acute cortical infarct, no intra-cerebral haemorrhage, no stroke mimic such as tumour, or subdural haematoma)... Investigators will post scans to the LACI-3 Imaging office in Edinburgh for central reading in DICOM format or upload them online to the database according to the imaging acquisition guidance.

In participants whose lacunar stroke occurred more than six months previously, or in whom there have been further neurological symptoms, any brain MRI or CT imaging performed in the interval between the index lacunar stroke and recruitment should also be sent for central reading.

Cognitive baseline testing: Participants will be assessed at baseline using the Montreal Cognitive Assessment (MoCA), and the timed Trail Making Test B for processing speed/executive function, and for the concentration, the backwards spelling from the MMSE.

The lifestyle risk factors for vascular disease such as cigarettes and alcohol use as well as blood pressure, weight and height will be collected as a part of the baseline information.

Participants will be asked about health-related quality of life (using the EuroQol Group EQ-5D-5L/ EQ-VAS instrument).

Haematology and biochemistry: Full blood count, urea and electrolytes and renal function results will be obtained and collected on e-CRF from the most recent standard of care results sample since the time of the index stroke. If there is a clinical reason to expect change since this last sample, the full blood count and biochemistry should be repeated prior to randomisation. These samples will be analysed in the hospital haematology or biochemistry labs in the centre in which the patient has been recruited as a part of the standard clinical care.

Clinical outcomes: Information on recurrent ischaemic stroke, TIA, major systemic or brain haemorrhage, non-fatal MI, and dementia will be assessed by phone or post questionnaire at 6, 12, and 18 months as well as by checking the participant's medical notes. Patients will be encouraged to seek medical advice if they develop new neurological events during the trial. The death of any cause will be detected, reported and recorded by the investigators based on the information from the medical notes.

Functional outcome: modified Rankin Scale to assess dependency at 6, and 12, 18 months. If participants are unable to be contacted, the central assessor will obtain the most recent modified Rankin Score from the local staff (if available) or estimate from the relative/carer.

Cognitive and mood outcomes: Telephone MoCA (tMoCA), The Telephone Interview for Cognitive Status (TICS), animal naming, Concentration (from the MMSE), the ZUNG and Stroke Impact Scale (SIS), will be collected remotely at 6, 12 and 18 months by the central trial team.

Drugs symptoms: Will be assessed by site investigators after randomisation at 1-2 weeks and 3-4 weeks visits and by the blinded central team at 6, 12 and 18 months using a short simple validated questionnaire to assess for symptoms potentially related to trial tablets as part of safety monitoring, including headache, dizziness, palpitations, altered bowel habit, falls, bruising and bleeding, as in LACI-2. The participant will be asked whether any symptoms were severe enough to interfere with normal daily activities. Participants will also be able to report any other symptoms and describe them in detail.

Drug adherence: Will be assessed by site investigators at each follow-up visit by phone. Participants will be asked about adherence to medication using a very short structured question. These contacts will be timed around prescribing for the next batch of IMP.

Blood pressure: Will be collected by the site hospital teams as a part of the baseline visit. BP measurements, if available, will be collected by sites as a part of the site phone follow-up at each follow-up visit. Sites can use self-recorded BP by the participant using their own BP monitor or self-reported from routine GP or other hospital measure. The medication list including antihypertensive drugs will be collected at each visit by the hospital team as a part of the data collection on the continuing routine stroke prevention therapy.

Health economics: EQ-5D-5L, EQ-VAS will be collected at 6, 12 and 18 months and measures to assess health economic usage and impact of trial drug (contact with health care, place of residence, return to work, etc) will be collected centrally at 18 months.

Repeat Brain CT or MRI: any repeat scanning performed to assess a recurrent neurological event during the trial will be anonymised and sent to Edinburgh for central blinded adjudication.

Follow-up:

After randomisation, all participants will be followed up for outcome and safety events until the end of their follow-up at the 18 months visit.

The follow-up includes five visits. Participants will be followed up remotely by phone and post for 18 months by two teams: the local site and the central research team. Each time, a questionnaire will be completed by a participant by telephone or on paper or both to collect trial outcomes.

Local site:

- Contact at one-two and three-four weeks by phone to advise on dose escalation, check symptoms and drug adherence, BP, outcomes and safety.
- Contact at 6, 12, 18 months by phone to check drug adherence; BP, medication history and supplements, outcomes and safety; arrange IMP re-supply by post if applicable

Central:

- Contact at 6, 12 and 18 months by post to collect recurrent vascular events, cigarettes and alcohol use, mRS, drug symptoms, Stroke Impact Scale, EQ-5D-5L, EQ-VAS, and health economic parameters only at 18 months; outcomes and safety
- Contact at 6, 12 and 18 months by phone to collect cognitive outcomes: tMoCA, TICS, Concentration (from MMSE), Animal naming, Zung, outcomes and safety

Central follow-up at 6, and 12, 18 months will be by post and telephone, blinded to allocated treatment. A trained assessor who is part of the central trial team and based either at the University of Edinburgh or University of Nottingham and who is blinded to treatment and baseline clinical information, will first confirm with the local site team and/or GP that the participant is contactable. They will then contact the participant by post and phone to administer the questionnaires following a standardised script.

About three weeks before the anniversary of the participant's randomisation or the last follow-up visit, the site hospital team will contact a participant by phone to conduct the 6, 12, or 18 months follow-up visit and to arrange the IMP re-supply if relevant.

If the site hospital team confirms that the participant is still alive, the participant will be sent a postal central follow-up questionnaire (followed by a telephone reminder if no response is received).

The central follow-up paper questionnaire can be obtained by phone during the cognitive outcomes collection. If the follow up information cannot be obtained by either postal or telephone questionnaire the local research team will be asked to provide follow up information from the medical records or by contacting the GP.

If, after at least 5 attempts, a participant fails to complete the phone visit done by the hospital site or return the paper questionnaire or will not complete the cognitive testing done centrally, this will be recorded as lost to follow-up in the e-CRF and reviewed by the TSC and DMC.

LACI-3 Protocol

Version 2.0, 16 December 2024 IRAS ID: 1008629

Table 2 Study Assessments

Follow-up ^b													
V2	/2 V:	/3 V4			V5				V6 ^c				
1-2 week	week 3-4 w	ek	6 months			12 months				18 months			
Site	ite Sit	e S	Site Central +/- 3 weeks				Site Centra		ntral	al Site		Central	
+/- 1	+/- 1 week				+/- 3 weeks			+/- 5 weeks					
Phone	one Pho	ne Phone	Post	Post	Phone	Phone	Post	Post	Phone	Phone	Post	Post	Phone
	1												
												٠	
•	• •	•				•				•			
		•				•				•			
			•				•						
•	•												
			٠				•						
										•			
•	• •			•				٠				•	
•	• •	•				•				•			
•	• •			•				•			•)	
										1			
				٠				•				٠	
					٠				٠				٠
•	• •			•				•			•)	
				٠				٠				٠	
					• • • •	• • • •	• • • • • • • • •		• •	• • • • • • • • • • • •	• • • • • • • • • • • • • • •	• • •	• •

^a Randomisation visit can take place on the same day as the consent visit at the clinic, if all required tests for eligibility criteria and the baseline information are available.

^b Participants will be followed up remotely by phone and post for 18 months by two teams: local site and the central research team.

^c End of Study Visit is a follow-up visit at 18 months.

^d Copy of the diagnostic scan (CT or MRI) will be sent for central reading.

⁶ Full blood count, urea and electrolytes and renal function will be obtained from the most recent sample since the time of the index stroke. ¹ Blood pressure collection is optional depending if a participant has access to the BP monitor or GP or hospital measure is available.

⁹ Dispensing in 3-monthly intervals is allowed. IMP re-supply to be sent to the participants home address.

^h Recurrent ischaemic stroke, TIA, major systemic or brain haemorrhage, fatal or non-fatal MI, death of any cause, dementia

¹ Modified Rankin Scale can be obtained from the relative/carer or the local site if a participant is unable to be contacted. ¹ Stroke Impact Scale (SIS), Telephone MOCA, Telephone Interview for Cognitive Status (TICS), concentration (from MMSE), Animal naming, ZUNG

* SAE - Serious Adverse Event; SAR - Serious Adverse Reaction, SUSAR - Suspected Unexpected Serious Adverse Reaction

¹EQ5D5L, EQ-VAS - quality of life questionnaires will be done at baseline and each follow-up visit. The NHS and social service use will be done at 18 months visit

^m Women of childbearing potential must have negative urine pregnancy testing on the day of randomisation. If applicable, the central team will send the urine pregnancy test with the central follow-up paper questionnaire.

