4.3 EXCLUSION CRITERIA

General exclusion criteria:

- Less than 24 hours since onset of the lacunar stroke or patient on dual antiplatelet drugs;
- Stroke mechanism with definite treatment indication (e.g. cardioembolism, ipsilateral carotid stenosis);
- Other explanation for the lacunar stroke symptoms (ie recent cortical infarct, haemorrhage or tumour);
- Other active neurological disease (e.g. brain tumour, multiple sclerosis, recurrent seizures, neurodevelopmental disorder well-controlled epilepsy present prior to the lacunar stroke, a single seizure at onset of the stroke, or provoked seizure, is not an exclusion);
- Contraindication to both trial drugs in section 4.3 of the SPCs (patients with a contraindication to one trial drug may still be randomised to the other trial drug);
- Indication for either trial drug (patient already prescribed one trial drug may still be randomised to the other trial drug);
- Dependent (mRS>2);
- Clinical diagnosis of dementia;
- Planned surgery during the trial period including carotid endarterectomy. Note prior and apparently successful carotid endarterectomy (or other surgery) is not an exclusion criterion and patients who would otherwise be eligible but require endarterectomy first may be randomised after recovery from successful endarterectomy;
- Unable to swallow;
- Diagnosis of hypotension, defined as sitting systolic blood pressure less than 100mmHg;
- History of drug overdose or attempted suicide

- Unlikely to be available for follow-up at 18 months;
- Unlikely to comply with study procedures and follow-up procedures for whatever reason (eg history of poor medication compliance) in the opinion of the randomising physician;
- Pregnant, breast-feeding, or of child-bearing potential and not using highly effective contraception as stated in section 10.9 (Pregnancy);
- Renal impairment (creatinine clearance <25 ml/min)
- Hepatic impairment
- Currently prescribed dual antiplatelet treatment (single antiplatelet is not an exclusion); patients can be randomised into the trial once the 28-day period of dual antiplatelet for guideline secondary prevention following the acute lacunar ischaemic stroke has completed;
- Previously enrolled in LACI-3;
- Enrolled in a study that precludes co-enrolment with LACI-3.

Cilostazol exclusion criteria (still allows randomisation to ISMN):

- Definite indication for (i.e. already prescribed) Cilostazol, or definite contraindication to Cilostazol as per SPCs section 6.1.8.

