Note that randomisation will be performed during normal office hours (09.00 - 17.00) and the trial allows for randomisation to occur any time beyond 24hrs after the stroke (if the eligibility criteria are met) with no upper time limit after the stroke. Therefore, in the event of computer failure (for example: server failure), the investigator will wait until the computer system is re-established to perform the randomisation. Normally, this would only be a few minutes to two hours. However, if this delay requires the patient to return on a separate occasion to collect the drugs, then a separate appointment will be made and the patient's travel expenses covered as per other trial visits or the drug supply may be sent by post for the next day delivery.

Patients will be randomised to one of the following at a 1:1 ratio as per Section 6.3:

- cilostazol versus no cilostazol
- ISMN versus no ISMN

resulting in a partial factorial comparison of cilostazol versus ISMN versus both drugs versus neither drug.

All participants will continue their usual prescribed guideline stroke prevention medication.

The randomisation algorithm will allocate a unique participant identifier which will be used to label the treatment pack containing the appropriate drug made up for the patient and dispensed by the local Pharmacy.

Participants with an indication for or contraindication to one of the trial drugs may still be randomised to the other trial drug. If a participant allocated to both trial drugs develops a contraindication to one of the trial drugs after randomisation into the trial, then they should discontinue that drug but continue to take the other trial drug. If a patient has to discontinue either or both drugs, they should continue to be followed up in the trial as planned (unless they withdraw from the trial). Patients should remain in follow up until the end of the trial follow up period, even if they discontinue trial drug, unless they withdraw from the trial. Drug discontinuation will be recorded.

The study will be performed open label. Placebo tablets are not available and masking by encapsulation is too complicated and expensive. However, blinding of outcomes is important to obtain unbiased information about tolerability, safety, and efficacy. As such, IMP adherence structured questionnaire and prescribed medications will be taken by site staff who are already unblinded to trial allocation, while ascertainment of the main cognitive and

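### The mRS fallback for participants who cannot be reached sets no date window, does not bar the baseline score, and lets unblinded site staff supply the score

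*Protocol*

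**What the plan says.** The routine route is central. Section 6.9 gives the masked central team this task: "Contact at 6, 12 and 18 months by post to collect recurrent vascular events, cigarettes and alcohol use, mRS, drug symptoms". The fallback, under Functional outcome in the same section, is that if the participant cannot be reached "the central assessor will obtain the most recent modified Rankin Score from the local staff (if available) or estimate from the relative/carer". A footnote to Table 2 repeats it with the sources in the other order: "Modified Rankin Scale can be obtained from the relative/carer or the local site if a participant is unable to be contacted". More generally, when neither post nor telephone yields follow-up information, "the local research team will be asked to provide follow up information from the medical records or by contacting the GP".

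The site's own later contacts are described as "Contact at 6, 12, 18 months by phone to check drug adherence; BP, medication history and supplements, outcomes and safety". The Table 2 footnote defining outcome events reads "Recurrent ischaemic stroke, TIA, major systemic or brain haemorrhage, fatal or non-fatal MI, death of any cause, dementia", so mRS is not among them.

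On masking, section 5.5.1 says that the adherence questionnaire and "prescribed medications will be taken by site staff who are already unblinded to trial allocation", and assigns the main cognitive and clinical outcomes to central co-ordinators who are masked. Section 6.9 adds that the central assessor is also kept unaware of baseline clinical information.

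**The concern.** The trial is open label, so masked ascertainment is its main protection against assessment bias. For participants who cannot be reached, the fallback can bypass that protection in two ways. Site staff may hand over the last score on file with no limit on its age. If that is the baseline score, the participant is recorded as not dependent because eligibility required it. Or site staff may score the participant afresh while knowing the allocation.

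Dependency (mRS above 2) is the first-listed secondary endpoint in section 2.2.2 and a component of the composite. Ordinal mRS enters the Global Clinical Outcome (section 9.2), and less dependency is among the supporting evidence that the Data Monitoring Committee may weigh for benefit (section 3). A site-supplied score also enters as observed data. It therefore drops out of the section 9.2 comparison of participants with and without mRS, which is the plan's own check for drop-out bias. This is a rule about data collection, so an analysis plan cannot fully repair it later.

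**Working it through.** **1. Which mRS does the protocol make a site hold?**
- Baseline: mRS is a minimisation variable (5.5.1), and mRS above 2 is an exclusion (4.3). Any baseline score is therefore 2 or lower.
- After baseline: the site contacts in 6.9 (weeks 1-2 and 3-4, months 6, 12 and 18) do not mention mRS. Nor do the site form lists in 7.2 for the same visits. In 7.2, mRS at months 6, 12 and 18 appears only on the central postal form.
- The only site score that the text requires is thus the baseline one. A later score exists only if routine care, the records or the GP supply it.

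**2. Does the fallback agree with the masking statements?** A fresh site score comes from staff described as unblinded, against masked ascertainment in 5.5.1. A baseline score passed to the central assessor conflicts with keeping that assessor unaware of baseline information. Neither route is excluded.

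**3. How many could be exposed?** The protocol gives no rate of participants who cannot be contacted for mRS. Two stated figures bracket it:
- The preceding trial retained 358 of 363 at 12 months (1.1): 358/363 = 98.6%, so loss is 1.4%. 1300 × 0.014 = 18.
- Section 9.1 allows up to 15% and cites 8-15%. 1300 × 0.08 = 104; 1300 × 0.15 = 195.

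The 15% is the allowance for losses and cross-overs on the primary cognitive outcome, so 195 is a ceiling borrowed from another endpoint.

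**4. Effect if every exposed participant received a baseline score, with equal loss and equal risk by arm.** Let u be the uncontactable share.

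Recorded risk = (1 − u) × true risk, so recorded risk difference = (1 − u) × true difference.

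The protocol gives no dependency rate. Assume 10% in controls and an odds ratio of 0.70, the size that 9.1 uses for the primary outcome:
- Treated odds = 0.70 × 0.10/0.90 = 0.0778; treated risk = 0.0778/1.0778 = 7.2%; true difference = 2.78 points.
- u = 8%: 0.92 × 2.78 = 2.56 points.
- u = 15%: 0.85 × 2.78 = 2.37 points (recorded risks 8.5% and 6.1%).

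Power for two proportions, two-sided 5%, 650 per group:

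| Handling at u = 15% | Power |
|---|---|
| Full data, no loss | 43.2% |
| Baseline carried forward | 37.4% |
| Those participants left out | 37.8% |

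Over assumed control risks of 5-20% with odds ratio 0.70 and equal risk among the uncontactable, carry-forward costs at most about 1.3 points of power against leaving them out. The largest gap is at 20% control risk: 59.6% against 60.9%.

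**5. When does it bias direction?** Assume a true risk of 10% in both arms, and loss of 15% in one and 8% in the other, all given baseline scores. Recorded risks are 0.85 × 10% = 8.5% and 0.92 × 10% = 9.2%. The odds ratio is (0.085/0.915)/(0.092/0.908) = 0.0929/0.1013 = about 0.92, although there is no true effect.

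**The case against.** A reader might infer that these participants will be recorded as not dependent. The text does not say so. The rule takes a site score only if there is one, and offers a relative or carer estimate as the alternative. The Table 2 footnote names the carer first. Both places join the sources with an or, so neither sets an order of preference. Section 6.9 lets sites use medical records or the GP, so a later score above 2 can surface. Section 9.2 plans to compare participants with and without mRS, so the authors expect some to be missing. All of this stands: carry-forward is permitted, not prescribed.

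The inference that sites hold no later mRS rests on lists that are not exhaustive. The baseline list in 7.2 names neither mRS nor NIHSS, though both are needed for minimisation. Section 3 says that site and central teams both assess outcomes from 6 months, and the Table 2 grid cannot be read in the text available. This lowers confidence, but the visit text and the follow-up form lists agree with each other.

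A reader might also multiply the exposed number by an assumed dependency rate, for example 30-60%, to count misclassified participants. The documents support no such rate, and the step also assumes that no carer, record or GP helps.

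Finally, the primary outcome does not use mRS, the power cost is slight, and 9.1 reports no differential loss in the preceding trial. That limits severity. It does not justify leaving an undated, unmasked source open.

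**Conclusion.** The point holds as a weakness in the collection rule. The fallback has no look-back limit, does not bar a baseline score that eligibility fixes at 2 or below, and lets unblinded staff supply the score. That conflicts with the protocol's own promises of ascertainment masked to treatment and to baseline information.

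Exposure is about 18 to 195 of 1300, the upper end being the primary outcome's loss allowance. How many would be misclassified cannot be derived. With equal loss and equal risk by arm, the worst case shrinks the dependency risk difference by the uncontactable share (1.4% to 15%) and costs almost no power beyond leaving those participants out. Bias in one direction needs differential loss, differential dependency among the lost, or scoring influenced by allocation. The power figures and the 0.92 rest on assumed dependency risks. Severity is minor to moderate: the endpoint is secondary, but it feeds the composite and Global outcomes.

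**What to change.** Amend the Functional outcome paragraph of section 6.9 and the Table 2 footnote so that they agree:

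1. Accept only information dated within the visit window, and never the baseline score.
2. Have the masked central assessor score mRS from an interview with the relative or carer. Under 5.2 and 7.2 the nominated contact's details are held only at the site, so the site must arrange the contact without disclosing allocation.
3. Failing that, have the site or GP send records from within the window with allocation redacted, and let the masked central assessor score them. Do not accept a score assigned by the site.
4. Otherwise treat mRS as missing at that visit.
5. Record the source and date of every mRS on the form, so that a sensitivity analysis by source is possible.

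The cost is protocol and form wording, some redaction, arranging carer contact through sites, and a few more missing mRS values. Those missing values may be informative, but they will be visible as missing and so covered by the drop-out check in 9.2. The change should be made before follow-up data accrue.

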clinical outcomes will be collected by central follow-up co-ordinators who are masked to treatment allocation. During the first month after the randomisation, when the IMP dose will be increased, the local hospital sites will ask about the IMP symptoms using structured questionnaire at one-two and three-four weeks. The central blinded trial co-ordinators will continue to ask participants about the IMP symptoms at 6, 12, and 18-months follow-up visits. A web-based system into which the participant can enter information directly may also be available for participants who are willing to use this method.

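### Section 5.5.1 gives the main clinical outcomes to masked co-ordinators, but unblinded site staff also collect outcome events at all five calls, and their reports count

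*Protocol*

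**What the plan says.** Section 5.5.1 explains that there is no placebo and that masked outcome collection is therefore important. It then divides the work. Adherence and "prescribed medications will be taken by site staff who are already unblinded to trial allocation", "while ascertainment of the main cognitive and" (the sentence runs on over a page break) "clinical outcomes will be collected by central follow-up co-ordinators who are masked to treatment allocation".

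Other parts of the protocol describe a different division:

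- Section 3, under measurement of outcomes, names both the local hospital teams and the central co-ordinators as assessors.
- Section 6.9, local site list, first month: "Contact at one-two and three-four weeks by phone to advise on dose escalation, check symptoms and drug adherence, BP, outcomes and safety".
- Section 6.9, local site list, later visits: "Contact at 6, 12, 18 months by phone to check drug adherence; BP, medication history and supplements, outcomes and safety".
- Section 7.2 puts an outcome and safety events item on the site form at weeks 1-2, weeks 3-4 and months 6, 12 and 18.
- Section 7.2 also lists the site research team among the sources of reported events, all of which go to the same adjudication process.

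The masked team collects vascular events by post, and outcomes and safety by phone, at 6, 12 and 18 months (section 6.9). Section 6.9 adds a check of the medical notes, and blinded central reading of any repeat scan done for a new neurological event.

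**The concern.** In a PROBE design, protection against observer bias depends on who looks for events as well as on who classifies them. A TIA or a minor stroke often comes to light because someone asked the right follow-up question. If the person asking knows the allocation, the depth of questioning, or the readiness to enter an event on the form, can differ by arm without intent. Adjudication sees only what was reported. It can reject a reported event, but it cannot recover one that nobody elicited.

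The endpoints at stake are recurrent stroke or TIA, MI, dementia as an outcome event, the composite, and the Global Clinical Outcome. A reader of section 5.5.1 alone would conclude that the main clinical outcomes come only from masked staff. The schedule and the forms do not deliver that.

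**Working it through.** The plan gives no figure to reproduce on this point, so the check sets the passages side by side.

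**Step 1. Who is masked.** Section 5.5.1 describes the sites as "site staff who are already unblinded to trial allocation" and the central co-ordinators as masked.

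**Step 2. Who asks about outcome events, and when** (sections 6.9 and 7.2).

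| Time | Unblinded site | Masked central team |
|---|---|---|
| Weeks 1-2 | phone, outcomes and safety | none |
| Weeks 3-4 | phone, outcomes and safety | none |
| Month 6 | phone, outcomes and safety | post and phone |
| Month 12 | phone, outcomes and safety | post and phone |
| Month 18 | phone, outcomes and safety | post and phone |

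Sites ask at 5 of 5 time points and masked staff at 3 of 5. Table 2 of the protocol is broken in the available text and was not used. The section 6.9 lists and the section 7.2 forms agree without it.

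**Step 3. The order at months 6, 12 and 18.** Section 6.9 places the site call about three weeks ahead of the due date. The central questionnaire is posted once the site has confirmed that the participant is alive. The unmasked questioning therefore comes first.

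**Step 4. Whether a site-only report counts.** Section 7.2 accepts reports from several sources, including the site, removes duplicates and adjudicates. Nothing requires that the masked contact also found the event, so a site-only report that passes adjudication enters the analysis.

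**Step 5. Whether the number of contacts differs by arm.** Section 6.9 applies the five follow-up visits to all participants, and the qualifier about applicability attaches to drug re-supply, not to the call. The only contacts in the text specific to participants on drug are the extra calls that section 5.5.2 allows as needed during drug introduction. Their number is not stated.

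**Step 6. Which endpoints are exposed.**

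- Primary score: the tMoCA, TICS and animal naming are collected by the masked team. The only route for unmasked information is the clinical dementia diagnosis that feeds the score (section 2.1.2).
- Recurrent stroke or TIA, and MI: exposed directly, because a site report can be the only source.
- Composite: exposed through its event components. Its dependency and cognitive components rest mainly on central collection.
- Global Clinical Outcome: exposed through its stroke and MI components.

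**The case against.** The strongest reply is that site questioning adds a source and replaces none. Masked assessors question participants in every arm at 6, 12 and 18 months with a standard script, and the notes are checked as well. For bias to arise, an event would have to be missed by the masked post, the masked phone call and the notes check, and then be picked up unequally by sites. Section 5.5.1 also speaks of the main outcomes, and section 3 openly names both teams. This stands as mitigation, and it is why the point is moderate. It does not resolve the conflict, because recurrent stroke and MI are main clinical outcomes on any ordinary reading and site-only reports still count.

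A second reply is that sites cannot simply stop asking. Section 10.2 has participants asked about adverse events and hospital admissions at every visit. Section 10 treats these same outcomes as the main safety data and exempts them from SAE reporting. This stands in full, and the fix keeps site questioning.

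Two stronger readings are tempting and are not supported.

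- *Unequal contact counts.* Section 6.9 says of the adherence contacts that "These contacts will be timed around prescribing for the next batch of IMP", and a table footnote says "Dispensing in 3-monthly intervals is allowed". A reader might infer extra site interviews at months 3, 9 and 15 for those on drug, giving 5 + 3 = 8 contacts against 5. But the contacts timed around prescribing are the scheduled visits, the footnote has re-supply sent to the home, and section 7.2 has no outcome form at 3, 9 or 15 months.
- *A quantified bias.* Suppose a true risk of 6% in both groups, with 80% of events detected off drug and 90% on drug. The observed risks are 0.06 × 0.80 = 4.8% and 0.06 × 0.90 = 5.4%, and the spurious odds ratio is (0.054/0.946)/(0.048/0.952) = 1.13. Exchanging the two detection rates gives 1/1.13 = 0.88. Every input is assumed. The protocol plans the study on no event risk and gives no detection rate, and a ten-point gap in overall detection takes little account of the masked questioning scheduled in all arms. The example shows only that the direction is open.

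**Conclusion.** The inconsistency is real. Section 5.5.1 gives ascertainment of the main clinical outcomes to masked staff, whereas sections 3, 6.9 and 7.2 have unblinded sites collect outcome events at all five calls, alone before month 6 and first thereafter. A residual risk of detection bias remains for recurrent stroke or TIA, the composite and the Global Clinical Outcome. The primary score is affected only through the clinical dementia diagnosis.

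The size and direction of any bias cannot be derived from the protocol. The conclusion rests on two readings of the text: that a site-only report, once adjudicated, counts as an outcome event, and that site staff know the allocation. It does not rest on any difference in the planned number of calls, which is the same in every arm.

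**What to change.** 1. Reword section 5.5.1 to agree with sections 3, 6.9 and 7.2: masked co-ordinators collect the cognitive and functional outcomes and ask about clinical events at 6, 12 and 18 months, and unblinded sites also report outcome events.
2. Keep site safety questioning at all five calls.
3. On the outcome event form, record every route by which each event was reported: masked central contact, site call, medical-notes check. A field for the first route only would not do, because the site call comes earlier and would be credited with most events.
4. Prespecify a sensitivity analysis of stroke or TIA, MI, dementia and the composite. It should count only events identified by the masked central contact or by a notes check done identically in all arms, whether or not a site also reported them. The details can go in the statistical analysis plan, but the route data must be captured prospectively because they may not be reliably recoverable later.

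The cost is a clarified paragraph, a small addition to the event form and one extra analysis. That analysis will contain slightly fewer events than the main one.
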